## 1.0 Background

Elbow fractures are complex injuries that often involve the articular surface, are in close proximity to critical neurovascular structures, and are prone to post-operative complications. Complications following treatment of intra-articular elbow pathology can affect over 50% of patients and up to 30% of all patients will require a re-operation. One of the most common complications is joint stiffness. When a flexion arc of motion is diminished to less than 100 degrees, a flexion contracture is present greater than 30 degrees, or forearm rotation is less than 100 degrees, functional limitations are frequently present and further treatment may be recommended. In fact, contracture release may be required in 12-20% of patients after intra-articular elbow fractures and carries a relatively high complication rate when performed.

The relationship of post-traumatic elbow contracture to intra-articular fractures is well established and can be caused by extrinsic factors such as heterotopic ossification (HO), fibrosis and capsular thickening, or by intrinsic factors such as failure of nonunion, malunion, arthrosis, or loose bodies. Recent studies analyzing the acute phase synovial fluid cytokine profile after an intra-articular elbow fracture have shown proinflammatory and catabolic factors in high concentrations that can lead to contracture through myofibroblast differentiation and proliferation. Furthermore, HO can limit range of motion in up to 40% of fractures and may also result from prolonged inflammation with elevated IL-1 $\beta$  and TNF- $\alpha$  levels.

## 2.0 Hypothesis and Specific Aims

### Primary Study Questions

- a. For adult patients (>18yo) who sustain intra-articular elbow fractures (radial head, proximal ulna, distal humerus, or combined) that undergo operative fixation, does perioperative glucocorticoid administration (IV intra-operative followed by a post-operative oral taper course) improve post-operative range of motion (flexion/extension and pronation/supination) compared to a placebo?

### Secondary Study Questions

- b. Is perioperative glucocorticoid administration more effective in improving range of motion for certain intra-operative elbow fractures or depending on the mechanism of injury (subgroup comparison based on fracture type and high-energy or low-energy injuries)?
- c. Do patients that receive perioperative glucocorticoids have a higher surgical site infection rate?

### Hypothesis

1. Alternative: In adult patients with intra-articular elbow fractures, peri-operative dexamethasone administration will improve post-operative active range of motion early ( $\leq 6$  weeks) and at final follow-up ( $\geq 6$  months).
2. Null: In adult patients with intra-articular elbow fractures, peri-operative dexamethasone administration will not improve post-operative active range of motion early or at 6 month follow-up.

### **3.0 Animal Studies and Previous Human Studies**

Prior investigators have sought to improve post-operative range of motion by modulating the inflammatory cascade. Desai et al. performed a retrospective review of 26 patients with a terrible triad injury (radial head fracture, coronoid fracture, and elbow dislocation) treated either with or without perioperative dexamethasone. The authors noted a significant improvement in the elbow arc of flexion ( $132.5^\circ$  vs  $105.5^\circ$ ) and in pronosupination ( $165.8^\circ$  vs  $132.2^\circ$ ) with no difference in infection rate. Other animal studies have shown improved range of motion and decreased fibrotic reactions after joint immobilization in subjects treated with dexamethasone compared to controls. Studies involving hip and knee arthroplasty have also shown a dose effect of dexamethasone in improving range of motion and reducing inflammatory cytokines. Currently, no prospective studies of intra-operative or post-operative glucocorticoid use in upper extremity intra-articular fractures exist.

### **4.0 Inclusion/Exclusion Criteria**

#### **Inclusion Criteria**

- All adults  $\geq 18$  years old with an intra-articular traumatic elbow fracture to be treated with operative intervention and a standardized post-operative rehab protocol
  - Intra-articular elbow fracture defined as:
    - Distal humerus
    - Proximal ulna
    - Radial head fracture
    - Combination fracture of two or more of the above
  - Radiographs present confirming intra-articular injury

#### **Exclusion Criteria**

- Patients with bilateral elbow fractures
- Patients with an altered mental status
- Pregnant
- Allergy or contra-indication to glucocorticoid administration
- Type 1 or Type 2 diabetes
- Pre-injury limitation in elbow range of motion (patient reported)
- Unable to provide consent for themselves

## **5.0 Enrollment/Randomization**

General inclusion/exclusion criteria will be used to determine patient eligibility for this study. Potential study participants will be identified when they present to Vanderbilt University Medical Center or Vanderbilt Orthopaedic outpatient clinics for operative treatment of their intra-articular traumatic elbow fracture.

### **In-person Consent Process:**

When a patient is determined to be eligible for the study, study personnel will approach the patient about taking part in the study. If the patient agrees to participate in the study, they will be provided with an informed consent document to review. The consent process will be conducted using either 1) a paper version of the appropriate consent form or 2) a REDCap-based electronic consent form. The electronic consent form has been developed in REDCap, a secure, web-based, HIPAA-compliant, data collection platform with a user management system. The REDCap-based electronic consent form can be accessed by research personnel using any electronic device. Eligible patients will be given an opportunity to ask questions about the study. If the patient agrees to participate in the study by signing the informed consent document, they will be provided with a copy of the signed consent form for their records.

### **Electronic Consent Process:**

In the event a potential study candidate is missed during a consultation ER or outpatient clinic visit, or research personnel are unavailable to consent in-person, study personnel will contact the subject by phone to notify them of their study eligibility and ask if they would be interested in taking part. If the subject is interested in taking part in the study, study personnel will send a link to the REDCap-based electronic consent form by e-mail. If the subject agrees to take part in the study after reading the informed consent document, there will be an option for them to electronically sign their name and date the informed consent document. Once they electronically sign the electronic informed consent document, they will be given an option to save or print the signed electronic informed consent documents for their files.

### **Mail Consent Process:**

If the subject does not wish to provide their email address, they will be sent two copies of the informed consent document by mail. If they agree to take part in the study, they will be asked to sign one copy and return it by fax or mail, and they will retain the second copy for their files.

### **Screening Form**

Once the patient has signed the informed consent document, the study team will document subject eligibility by completing the REDCap Screening Form. This step will ensure only eligible patients are included in the study. The REDCap screening form will be completed prior to randomization activities.

### **Enrollment Goal**

We will seek to enroll 18 patients in each treatment arm per fracture type and 18 patients in each control arm, for a total of 144 patients.

Fracture Type	Treatment Arm	Control Arm	Total
Distal humerus fracture	18	18	36
Radial head	18	18	36
Proximal ulna	18	18	36
Combined	18	18	36
			144

### **Randomization**

Patients will be randomized according to a stratified permuted block randomization with a block size of 4. Randomization will be stratified based on fracture type: radial head, distal humerus, proximal ulna, combined. Treatment A will receive glucocorticoid and Treatment B will receive placebo. There will be 9 total blocks per fracture type, for 36 patients in each fracture-type strata and an even balance in all 4 strata, for 18 in each treatment arm.

Randomization will take place after consent. A randomization allocation table will be uploaded into REDCap. Randomization will be conducted by an Orthopaedic research coordinator. The treating physician, study research coordinator and patient will be blinded to the treatment assignment.

## **6.0 Study Procedures**

### **Enrollment Visit**

In addition to the enrollment and randomization procedures noted in Study Protocol Item 5.0, patient demographics and injury information will be documented as part of the patient's baseline assessment. Patient demographics will be imported from eStar into the REDCap database using the REDCap Clinical Data Interoperability Services (CDIS) tools.

### **Operative Visit**

Preoperative-

Patients will be counseled regarding the possible adverse effects of the methylprednisolone and will be instructed to stop taking the drug immediately if they begin to experience the following adverse effects: skin rash, vision problems, muscle weakness, swollen face. The total dose up to stoppage will be recorded.

### **Intraoperative-**

Patients will receive either a single intraoperative dose of 10mg of intravenous dexamethasone (Treatment A) or a single intraoperative dose of 10 mg of saline (Treatment B) based on their randomization allocation.

### **Postoperative**

#### **Discharge or Hospitalization**

Following surgery, the participant will be provided with either a 1) six-day oral methylprednisolone taper course (Treatment A) or a six-day placebo course (Treatment B). Both medications will be in identical packaging. If the patient is admitted to the hospital following surgery, they will take the taper or placebo course as a home medication.

Day 0 (Day of surgery): 24mg oral dose, once daily

Day 1: 20mg oral dose, once daily

Day 2: 16mg oral dose, once daily

Day 3: 12mg oral dose, once daily

Day 4: 8mg oral dose, once daily

Day 5: 4mg oral dose, once daily

Day 6- Patients will be contacted by phone to assess compliance and experience (adverse effects).

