### **Follow-up Clinic Visits**

Based on routine care, patients will follow-up in the outpatient clinic at the following post-operative intervals: 2-week, 6-week, 3-month, and 6-month follow-up. The following data points will be collected at the routine care appointments:

- Active range of motion measurements by treating surgeon using a universal goniometer
  - Flexion/extension arc (degrees)
  - Pronation/supination arc (degrees)
- Surgical site infection requiring treatment (antibiotics or debridement: Y/N)
- Revision surgery (Y/N)
- Numeric pain score (0-10)
- Patient reported outcome Quick Disabilities of the Arm, Shoulder and Hand (QuickDASH) score
- Radiographic evidence of heterotopic ossification (present Y/N)
- Other complication not requiring revision surgery (nonunion, malunion, hardware failure, neuritis, synostosis)

If a participant misses a routine care postoperative visit or if the research coordinator is not available on site the day of the subject's appointment, the research coordinator will

attempt to contact the patient by phone, mail or electronically using REDCap, to obtain the outcomes data.

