## **7.0 Risks**

### **Side effects that can come from taking Dexamethasone or Methylprednisolone:**

- upset stomach
- stomach irritation
- vomiting
- headache

- dizziness
- insomnia
- restlessness
- depression
- anxiety
- acne
- increased hair growth
- easy bruising
- irregular or absent menstrual periods
- skin rash
- swollen face, lower legs, or ankles
- vision problems
- cold or infection that lasts a long time
- muscle weakness
- black or tarry stool

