### **Safety Monitor**

The Principal Investigator will designate a Safety Monitor for this study. The Safety Monitor will not be involved in the study work and will work independently of the Principal Investigator. The Safety Monitor will be provided reports by the statistician every 6 months, from first subject enrollment, and make a determination on the continuance of the study based on reports of adverse events and protocol deviations.

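### In the available text, drug adverse effects are asked about once, on Day 6; the later visits ask about none of the listed steroid effects except treated surgical site infection.

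*Protocol*

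**What the plan says.** Protocol section 6.0, Discharge or Hospitalization, sets out a six-day oral course that ends with "Day 5: 4mg oral dose, once daily". The next line is the safety contact: "Day 6- Patients will be contacted by phone to assess compliance and experience (adverse effects". It specifies no checklist or form of question, and no step for a patient who cannot be reached.

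Follow-up Clinic Visits then schedules "2-week, 6-week, 3-month, and 6-month follow-up" and opens its itemised list with "The following data points will be collected at the routine care appointments". One item on the list is a steroid harm: "Surgical site infection requiring treatment (antibiotics or debridement: Y/N". The rest are motion, pain, QuickDASH, revision surgery, heterotopic ossification and a category for other complications, whose bracketed examples are all surgical or fracture-related.

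Section 7.0 lists 19 side effects of the two steroids, including "cold or infection that lasts a long time" and "irregular or absent menstrual periods", without onset times. Section 8.0 requires study-related drug events to be notified to the principal investigator. Under Safety Monitor in section 9.0, an independent monitor receives six-monthly reports and is to "make a determination on the continuance of the study based on reports of adverse events and protocol deviations".

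**The concern.** The one scheduled inquiry comes a day after dosing stops, while contact with patients continues for months. An effect that starts or becomes recognisable after Day 6 enters the data only if the patient or surgeon raises it and someone attributes it to a drug whose identity is blinded. Spontaneous reporting of this kind is usually incomplete and uneven between surgeons.

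Two uses of the data are affected. The Safety Monitor's decision on continuation depends on adverse-event reports, and for late drug effects those reports would be unsolicited. In the final report, a low count of late effects could not be told apart from not having asked. The trial is placebo-controlled, with 4 × 18 = 72 patients planned per arm, so a fair comparison of the arms is available if the same question is put to everyone.

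**Working it through.** There is no planned figure to reproduce. The check is day arithmetic and a comparison of the risk list with what is collected.

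1. **Timing of the call.** Doses run from Day 0 to Day 5 and the call is on Day 6, so the gap is 6 − 5 = 1 day. The call follows the last dose and can cover the whole exposure period.

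2. **Contacts after the call.** Taking the visits as days 14, 42, 91 and 182 (an assumed conversion of weeks and months), they fall 14 − 6 = 8, 42 − 6 = 36, 91 − 6 = 85 and 182 − 6 = 176 days after the call. All four are existing contacts with a data list.

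3. **Risk list against visit list.** Section 7.0 has 19 entries. The infection entry is partly covered at the visits, by treated infection at the surgical site. A cold, or an infection elsewhere, is not covered. The other 18 entries have no item in the visit list.

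4. **What Day 6 can establish.**
   - *Prolonged cold or infection.* One that begins after the intraoperative dose has lasted at most 6 days at the call. Long duration is part of the entry's definition, so it cannot be established then.
   - *Menstrual change.* If cycles last 28 days and are evenly spread, a period falls due within Days 0 to 6 for 7/28 = 25% of menstruating participants. With cycles of 21 to 35 days the range is 7/21 = 33% to 7/35 = 20%. The cycle lengths are assumptions. The effect would often be missed by Day 6, but not always.
   - *Remaining entries.* The documents give no timing. They support saying that some may not show by Day 6, and no more.

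5. **Missed contacts.** For a missed clinic visit the protocol provides contact by phone, mail or REDCap. It states no equivalent for the Day 6 call, so a patient not reached has no solicited record of drug effects.

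6. **Analysis.** The dichotomous secondary endpoints in protocol section 10.0 are infection, revision, heterotopic ossification and other complication. The SAP plans logistic models for a second aim covering complications and safety, but neither document defines a drug adverse-effect variable for them.

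**The case against.** The strongest reply is that the course is short, the call comes after the last dose, and the one steroid harm the protocol set out to test is followed properly. Surgical site infection is secondary question c, is recorded at every visit to 6 months and is compared by arm. Patients are also counselled before surgery, drug events must be reported with no time limit, an independent monitor reviews reports, and the SAP mentions safety outcomes.

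Most of this stands, and it limits the point. A reader might infer that the later visits carry no adverse-effect item at all; the infection item shows otherwise. A reader might also infer that acne, hair growth and menstrual change cannot appear by Day 6; without onset times, the documents support only that they may not. Nor can the solicited days be divided by the length of follow-up to size the loss. Follow-up was set for motion and surgical outcomes, and that ratio does not measure the share of drug effects missed.

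What the reply does not supply is a scheduled question after Day 6. Counselling, section 8.0 and the Safety Monitor all depend on someone coming forward, and the SAP's safety outcomes are undefined.

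**Conclusion.** The point holds in limited form. One scheduled inquiry covers drug adverse effects, one day after the last dose. Of 19 listed effects, one is partly followed at later visits through treated surgical site infection, and 18 are not asked about again. By wording alone, one listed effect cannot be established on Day 6; for the others the timing is unknown. The number of events that would be missed cannot be estimated from the documents.

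The primary endpoint is unaffected and no stated rule or number is wrong, so this is an inexpensive improvement to safety ascertainment. The conclusion is confined to the available text: a portion of the protocol between Unmasking and section 7.0 was not available, and the point would fall if it schedules later questions about drug effects.

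**What to change.** - **Section 6.0, Day 6 call:** specify a short adverse-effect question based on the section 7.0 list, in a fixed form. The protocol describes no such instrument now, so it has to be written.
- **Section 6.0, Follow-up Clinic Visits:** add the same question at 2 weeks and preferably at 6 weeks. Patients not reached on Day 6 answer it at the 2-week visit. Once it is on the visit list, the existing phone, mail or REDCap fallback can serve it too.
- **Section 10.0 and the SAP:** add a table by randomised arm of the number of patients with each effect, and state which variables the SAP's safety outcomes comprise.
- **Section 9.0, Safety Monitor:** include that table in the six-monthly report.

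The cost is drafting one short form, a few minutes at one or two existing visits, and one extra table. More non-specific events will be recorded in both arms; with blinded, identical questioning they can be compared between arms.

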### **Follow-up Clinic Visits**

Based on routine care, patients will follow-up in the outpatient clinic at the following post-operative intervals: 2-week, 6-week, 3-month, and 6-month follow-up. The following data points will be collected at the routine care appointments:

- Active range of motion measurements by treating surgeon using a universal goniometer
  - Flexion/extension arc (degrees)
  - Pronation/supination arc (degrees)
- Surgical site infection requiring treatment (antibiotics or debridement: Y/N)
- Revision surgery (Y/N)
- Numeric pain score (0-10)
- Patient reported outcome Quick Disabilities of the Arm, Shoulder and Hand (QuickDASH) score
- Radiographic evidence of heterotopic ossification (present Y/N)
- Other complication not requiring revision surgery (nonunion, malunion, hardware failure, neuritis, synostosis)

If a participant misses a routine care postoperative visit or if the research coordinator is not available on site the day of the subject's appointment, the research coordinator will

attempt to contact the patient by phone, mail or electronically using REDCap, to obtain the outcomes data.

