## **10.0 Statistical Considerations**

### **Sample Size Justification**

Prior studies suggest Flexion/extension arc after intra-articular fracture  $\sim 105^\circ$ . Difference suggested by prior retrospective study with dexamethasone shows potential improvement ( $\delta$ ) of  $27^\circ$  (avg post-operative AROM  $132.5^\circ$ ). Conservatively, will attempt to see an improvement of  $25^\circ$  ( $\delta$ ). Average standard deviation from literature of post-operative intra-articular elbow fractures range of motion is  $17^\circ$  ( $\sigma$ ). A total of 22 patients are needed (11 treatment and 11 control) to be able to reject the null hypothesis with 90% power and  $\alpha = 0.05$ . Assuming a 20% loss to follow-up based on prior studies ( $\sim 10\%$ ) + non-compliance of six-day home taper course. As we are stratifying our treatment and control groups based on fracture type, we will need 18 patients in each treatment arm for each fracture and 18 patients in each control arm.

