### **Statistical Analysis**

- a. Primary analysis
  - i. Intention-to-treat
  - ii. Baseline characteristics between treatment arms will be compared using univariate descriptive statistics.
  - iii. Primary end-point (range of motion: continuous variable) → Univariate analysis of unmatched, interval variable with two groups assuming non-normal distribution: Mann-Whitney U Test will be performed.

- iv. Secondary end-points that are dichotomous (infection, revision surgery, heterotopic ossification, and other complication) will be analyzed with a chi-square or Fisher's exact test where the assumptions for a chi-square test are not met.
- v. Secondary end-points that are nominal or ordinal (Pain score, DASH score) will be analyzed using a Mann-Whitney U Test.

b. Subgroup analysis

- i. Analysis will be performed based on fracture type and stratification will make comparison possible.
- ii. Multivariate analysis using linear regression for the interval variable (range of motion) will be performed based on:
  1. Age <65 vs Age >65
  2. Mechanism of injury (High-energy vs. Low-energy)
  3. Treatment type
  4. Time from injury to surgery

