We will use the open-source statistical package R (R Development Core Team, 2012) and Stata 16 statistical software (StataCorp LLC, 2019, College Station, TX) for analysis. An intention-to-treat analysis will be conducted including all eligible patients as originally randomized. Analysis of each primary and secondary endpoint will be performed with all patients at each follow-up time point. Interactions for fracture-type and treatment group will be modeled at each follow-up time point and if significant, each fracture-type group will be independently analyzed. Multivariable proportional odds models for the Aim 1 dependent variable, range-of-motion, will be performed and multivariable logistic regressions will be performed for Aim 2 outcomes evaluating complications and safety. The Aim 3 dependent variable is continuous MME total and will be analyzed using a multivariable proportional odds model as the total amount consumed for each patient during the post-operative course.

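### The other-complication endpoint excludes cases that went to revision and no reason for revision is listed, so no planned analysis gives the total of nonunion, malunion, hardware failure, neuritis or synostosis by arm

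*Protocol*

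**What the plan says.** Protocol section 6.0, Follow-up Clinic Visits, lists the data collected at 2 weeks, 6 weeks, 3 months and 6 months. Three items matter here:

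- "Other complication not requiring revision surgery (nonunion, malunion, hardware failure, neuritis, synostosis"). The five named complications count only when they did not lead to revision.
- "Revision surgery (Y/N"). No reason for the revision is listed.
- "Surgical site infection requiring treatment (antibiotics or debridement: Y/N"). Treated infection counts whether or not it was managed surgically. Heterotopic ossification, in the same list, is likewise recorded without reference to revision.

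Protocol section 10.0, Statistical Analysis, item a.iv: "Secondary end-points that are dichotomous (infection, revision surgery, heterotopic ossification, and other complication) will be analyzed with a chi-square or Fisher's exact test". Each endpoint is named separately and no combined endpoint is defined.

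The SAP adds that "multivariable logistic regressions will be performed for Aim 2 outcomes evaluating complications and safety". It does not itemise the Aim 2 outcomes. It analyses endpoints at each follow-up time point, and the population is all randomised patients: "An intention-to-treat analysis will be conducted including all eligible patients as originally randomized".

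**The concern.** A nonunion that is left alone is an other complication, while one that is re-operated is not. Where a patient is counted therefore depends on a decision taken after randomisation, and the item excludes the cases serious enough to need surgery. All randomised patients stay in the denominator, so intention-to-treat is not broken. The difficulty is what the numerator means.

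Two things follow. First, the simplest safety question about these events, namely how many patients in each arm had a nonunion, malunion, hardware failure, neuritis or synostosis, has no planned answer. Second, the between-arm test of the item compares only the unrevised remainder. That remainder understates any difference and can point the wrong way if the two arms differ in the share revised. The revision endpoint helps, but it pools surgery for failed healing or hardware with surgery for other reasons, possibly including release for stiffness, which the trial hopes to reduce.

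**Working it through.** **Plan's own figure.** The documents give no expected rate or sample size for this endpoint. Their only calculation is for range of motion: 25° difference, SD 17°, 90% power, alpha 0.05, 11 per arm. A two-sided two-sample t-test reproduces it (10.78, rounded up to 11; power 90.6% at 11). It does not bear on this point.

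**Where a case is counted under the current definitions**

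| Event | Other complication | Revision | Total for that complication |
|---|---|---|---|
| Nonunion, not revised | yes | no | not available |
| Nonunion, revised | no | yes, no reason listed | not available |
| Treated infection, with or without debridement | own field | if revised | available |
| Heterotopic ossification, revised or not | own field | if revised | available |

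Only the five structural and nerve complications are split in this way.

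**Effect on the comparison.** Let c be the true proportion with a listed complication and s the share of those revised, for arms A (worse) and B. Then:

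- other complication = c(1 − s)
- structural revision = c × s

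The arms contain 4 × 18 = 72 patients each, before any loss to follow-up. All values of c and s below are assumptions. Power is for a two-sided comparison of two proportions at 0.05.

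| c, A v B | s, A v B | Other complication, A v B | Structural revision, A v B |
|---|---|---|---|
| 25% v 20% | 20% v 20% | 20% v 16% | 5% v 4% |
| 25% v 20% | 50% v 20% | 12.5% v 16% (power 9%) | 12.5% v 4% (power 46%) |
| 20% v 20% | 60% v 20% | 8% v 16% | 12% v 4% |

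Row 1 is dilution: the 5-point difference becomes 4 points, in the right direction. Row 2 is reversal on this one item, with revision pointing the other way. In row 3 the totals are equal and the item still shows a difference.

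**When reversal occurs.** It needs c_A(1 − s_A) < c_B(1 − s_B). At 25% v 20% with s_B = 20%, that is 1 − s_A < 0.16/0.25 = 0.64, so s_A must exceed 36%.

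**The same in assumed counts.** Suppose nonunion occurs in 8 v 4 of 72, with 6 and 1 revised.

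- Other complication: 8 − 6 = 2 v 4 − 1 = 3 (Fisher p = 1.0)
- Revised nonunion: 6 v 1 (p = 0.12)
- Total: 8 v 4 (p = 0.37)

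**How well revision serves as a backstop.** Take row 2 and add contracture releases in 8% v 16% of patients, with no overlap. The 16% is the midpoint of the 12–20% in section 1.0 Background; the 8% is assumed. Total revision is 12.5 + 8 = 20.5% v 4 + 16 = 20.0%, and no difference shows on either endpoint.

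**How many cases could move.** Background says that complications "can affect over 50% of patients and up to 30% of all patients will require a re-operation". Taking 50% and 30% as working values, and assuming every re-operation is in a patient with a complication, up to 0.30/0.50 = 60% of patients with a complication could be revised. That is about 22 of 36 per arm (0.30 × 72 = 21.6; 0.50 × 72 = 36). This is an outer bound over all complications, not an estimate for the five listed here.

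**The case against.** A reader might infer that the worst cases vanish from the trial, so that an arm with more severe failures would look safer overall. The documents do not support that. A revised nonunion moves to revision surgery, a more serious category that is tested as its own secondary endpoint. The two items divide cases by whether revision was needed.

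Several further objections stand:

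- Reversal needs a higher revised share in the worse arm. Nothing in the documents suggests one, and the treating physician is blinded. Where such a gap did arise, structural revision would show it: 6 v 1 in the counts above is the clearest signal in the example and points towards harm.
- Cancellation by contracture releases needs a second assumption. The 12–20% in Background has no time frame, follow-up ends at 6 months, and the protocol does not say whether a release counts as revision.
- The protocol's list of steroid side effects does not include nonunion, malunion or hardware failure. The safety question it poses is surgical site infection, and that item does not have this defect.
- Infection-related revisions can largely be identified by crossing the infection and revision fields.
- The case report form is not among the documents. It may hold a reason for revision, and the clinical record may allow one to be recovered.
- The total would not be well powered either: about 11% for 25% v 20%, and p = 0.37 for 8 v 4.

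These points limit the size of the concern without removing it. The listed items and planned analyses still give no total for the five complications. Recovering the reason from records afterwards is possible but unplanned. Low power is a reason to report a count that can be interpreted, not a reason to keep one that cannot. Nor does collection at four visits settle the matter: no rule says how to code, at 6 months, a nonunion recorded at 3 months and revised in between.

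**Conclusion.** The point holds as a definition and reporting gap in one secondary safety endpoint. As written, the plan yields no total of nonunion, malunion, hardware failure, neuritis or synostosis by arm, and this follows from the definition itself. The other-complication comparison is diluted when the arms have equal revised shares and can mislead when the shares differ. The revision endpoint is a partial backstop because it pools reasons for surgery.

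The reversal and the cancellation are illustrations under assumed rates. They show what the definition permits and do not predict what this trial will find. It would go too far to conclude that the safety analysis as a whole is biased in favour of the steroid. The primary endpoint, the sample size and the infection and heterotopic ossification comparisons are unaffected.

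**What to change.** In protocol section 6.0, Follow-up Clinic Visits:

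- Remove the restriction to unrevised cases from the other-complication item.
- Record each of the five listed complications yes/no, whether or not it is revised.
- Add a reason-for-revision field, for example stiffness, infection, nonunion or hardware, other.
- State that a complication once recorded stays recorded if it is later revised.

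In protocol section 10.0, item a.iv, and among the SAP's Aim 2 outcomes:

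- Analyse any listed complication, revised or not, once per patient.
- Keep revision surgery as its own endpoint.
- Tabulate revisions by reason and arm.

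The cost is a wording change, one extra form field and a little more analysis, with no added visits or patients. The complication and revision endpoints will then overlap, since a revised nonunion counts in both, and the report should say so.
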